4. OBSERVATIONAL STUDY DESIGN

Multicenter, observational, prospective clinical study. Data from the first 500 patients enrolled in the registry will be used for the present analysis. Please see point #3 of the present protocol for information regarding registry enrollment criteria and data collection.

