3. REGISTRY DESIGN

The creation of the present registry is aimed at gathering information on a wide cohort of patients affected by ES. All patients will be enrolled for a minimum of three years from the protocol approval. There is no pre-specified date for the end of enrollment, which will be decided by the study responsible according to the enrollment rate.

A minimum of 500 patients will be included in the present registry. The exploratory nature intrinsic to the registry characteristics does not allow a sample size calculation by statistical means. However, the sample presented is based on the estimated enrolment rates of the participating centers during a 3-year enrolment period. Moreover, the sample size is large enough to postulate specific subgroup analyses.

REGISTRY INCLUSION CRITERIA:

- Diagnosis of ES (documentation of 3 or more episodes of sustained ventricular arrhythmia within 24h or documentation of sustained ventricular tachycardia lasted at least 12h). In order to fulfill this criterion, a patient with a previous episode of ES could also be enrolled during routine screening.
- Age ≥ 18
- Written informed consent

REGISTRY EXCLUSION CRITERIA:

- patient without ICD
- Confirmed or suspected use of drugs or narcotics with known direct pro-arrhythmic effect
- Inability to express an informed consent for the study

At enrollment, each patient will be informed on the aim and the design of the study, and the investigations needed. All patients that meet the inclusion criteria will be included in the study (attachment #1). All recruited patients will receive the informative form (attachment #1) and the informative letter to their general practitioner (attachment #2).

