3.1 EVALUATION OF ELIGIBILITY

All patients admitted to the participating centers will be evaluated consecutively by the referent investigators. All patients that meet the above-described criteria will be included in the registry.

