3.2 DATA COLLECTION

No additional procedures are required to the participating centers. Data usually collected in the center and necessary for the analysis will be collected by the referent investigator. Considering that ICDs record the principal events of the whole life of the device, patients with an ES previous to the creation of this registry will be included retrospectively providing that:

- 1) clinical data from the participating center are complete and accurate and allow to check inclusion and exclusion criteria
- 2) follow-up is available
- 3) ICD has not been replaced, leading to the loss of original data
- 4) ECG and echocardiography done in routine practice are available in case of necessity
- 5) subject agrees to subscribe the informed consent during the next routine visit in the recruiting center

All data will be used with scientific research purposes only. Data will be saved on a dedicated website⁷ in agreement with current regulations on the treatment of personal data. Electronic cards of data collection transmitted to the study responsible will be identified by an alphanumeric code. The list of matches between subjects' data and these codes will be created and kept by local investigators or delegates. The data manager is the study responsible.

For the type of data requested, see Case Report Form (attachment #3)

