Attachment #3- Case report form

 
Università Politecnica delle Marche - Clinica di Cardiologia Case Report Forms ELECTRA

Fill in following fields and "Enter"

0.1 - General Data
 
Last name  - First name  - Sex  - Birth date  Height (m)  - Weight (kg)  - NYHA 

0.2 - Risk factors and comorbidities
 
Hypertension  - Diabetes mellitus  - Previous Stroke or TIA  - Atrial Fibrillation  Previous episode of documented myocardial ischemia  - Peripheral artery disease 

0.3 - Chronic medical therapy (pre-storm)
 
Amiodarone  - Beta-blockers  - Ranolazine  Antiarrhythmic drugs class 1A  - Antiarrhythmic drugs class 1B  - Antiarrhythmic drugs class 1C  - Sotalol  - Digoxin 

0.4 - Laboratory exam
 
Haemoglobin (g/dl)  - Hematocrit (%)  - Creatinine (mg/dl)  - BNP (ng/dl)  - Kaliemia (mEq/l)  - Magnesemia (mEq/l) 

0.5 - Echocardiography (acute phase)
 
Ejection fraction (%)  - End-diastole interventricular septum (mm)  - End-sistole interventricular septum (mm)  Left ventricular diastolic diameter  - Left ventricular systolic diameter  - End-diastole posterior wall (mm)  - End-sistole posterior wall (mm) 

1.1 - ICD data
 
ICD type  - Implantation date  - Prevention  - Cardiomyopathy  ICD Brand  - ICD Model 

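### Enrolment is not tied to a date, and the case report form shows no consent date or entry mode, so patients who enter alive after a past electrical storm cannot be properly separated or adjusted for in the 3-year mortality estimate.

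*Combined protocol and SAP*

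**What the plan says.** Section 4 takes the analysis set from the registry by order: "Data from the first 500 patients enrolled in the registry will be used for the present analysis". Section 3 gives a floor and no ceiling: "A minimum of 500 patients will be included in the present registry", and "There is no pre-specified date for the end of enrollment". The number enrolled can therefore pass 500.

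There are three ways in:

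- **New admissions.** Section 3.1: "All patients admitted to the participating centers will be evaluated consecutively by the referent investigators".
- **Earlier ES found at routine screening.** The first inclusion criterion in section 3 allows this.
- **ES before the registry existed.** Section 3.2: "patients with an ES previous to the creation of this registry will be included retrospectively providing that" five conditions are met. One of these is agreement to sign consent at the next routine visit.

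Written consent is an inclusion criterion for everyone. Section 3 describes what happens at entry ("At enrollment, each patient will be informed on the aim and the design of the study") but does not name the date that counts as enrolment.

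Section 3.2 points to Attachment #3 for the data requested. Its dates are birth, ICD implantation, ES start and end, ablation, last follow-up, and first recurrence of ES, of VT/VF and of heart failure admission. Attachment #4 repeats the follow-up items. Neither shows a date of enrolment or consent, or a field for the route of entry.

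Section 4.1 sets the primary endpoint as death from any cause at three years, with the clock starting at the ES. Section 4.4 reports it as counts and percentages, with Kaplan-Meier curves and log-rank tests. It does not mention late entry.

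**The concern.** Two things follow from the missing date.

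The lesser one is that the rule for choosing the 500 cannot be applied or audited from the listed data items, because nothing in them ranks patients across centres.

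The greater one concerns the estimate itself. A patient who consents some time after the ES has, by design, survived that interval. Patients who died in the same interval could not consent and are absent. If such patients are counted from the ES as though observed throughout, they add survival time in which they could not have died, and mortality comes out too low. The standard correction places each patient in the risk set only from the date of entry. That date is not among the listed items. Section 4 calls the study prospective, but the listed data could not show what share of the 500 was observed prospectively.

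**Working it through.** **The plan's own figures.** Section 4.4 uses 11% a year and 500 patients.

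- One year: 500 × 0.11 = 55, as stated.
- Three years: 500 × 0.11 × 3 = 165, as stated. This is a simple product that ignores the shrinking number at risk. Compounded, it is 500 × (1 − 0.89³) = 147.5 deaths, or 29.5%. The compounded form is used below.

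**Assumptions that the documents do not give.** Late entrants join one year after the ES and face the same 11% a year. New admissions enter at the ES. Late-entrant shares of 20% and 60% are illustrative.

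**Mortality counted from the ES, by route.**

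- New admission: 1 − 0.89³ = 29.5%.
- Late entrant, alive at one year by design: 1 − 0.89² = 20.8%.

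**Pooled percentage, as section 4.4 would report it.**

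- 20% late: 0.8 × 29.5 + 0.2 × 20.8 = 27.8%.
- 60% late: 0.4 × 29.5 + 0.6 × 20.8 = 24.3%.

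The two differ by 3.5 points. The 95% sampling margin at n = 500 is 1.96 × √(0.295 × 0.705 / 500) = 4.0 points.

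**Other shares and delays** (same 11%; expected deaths among 500, with 147.5 or 29.5% if nobody enters late):

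| Late share | Delay 0.5 year | Delay 1 year | Delay 2 years |
|---|---|---|---|
| 10% | 145.4 (29.1%) | 143.2 (28.6%) | 138.3 (27.7%) |
| 25% | 142.2 (28.4%) | 136.6 (27.3%) | 124.4 (24.9%) |
| 50% | 136.9 (27.4%) | 125.7 (25.1%) | 101.3 (20.3%) |

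**Does an entry date repair it?** Take 20% late at one year.

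- Year 1: 400 at risk, 44.0 deaths, 356 left.
- Year 2: 356 + 100 = 456 at risk, 50.2 deaths, 405.8 left.
- Year 3: 405.8 at risk, 44.6 deaths.

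The raw percentage is 138.8 / 500 = 27.8%. With late entrants at risk only from entry, survival is (1 − 44.0/400) × (1 − 50.2/456) × (1 − 44.6/405.8) = 0.89³, so mortality is 29.5%, the value with no late entry.

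The price is precision. Greenwood's formula, 1.96 × S × √Σ d/[n(n − d)] with S = 0.705, gives ±4.1 points here. At 60% late the at-risk numbers are 200, 478 and 425.4, with 22.0, 52.6 and 46.8 deaths, and the margin is ±4.7 points.

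**What the listed dates can do.** The ES start date, set against the registry's start, picks out storms that predate the registry. It does not pick out a storm after that start whose patient was enrolled later at routine screening. It does not give the delay from ES to entry for either group.

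**The case against.** A reader might infer that membership of the 500 depends on the order in which records are typed in, and that centres could load past-storm patients in bulk to fill the set. The documents do not support this. Section 3 makes written consent an inclusion criterion, section 3.1 has admitted patients evaluated consecutively, and section 3.2 ties each retrospective patient to consent at a routine visit. Order of consent is the natural reading, and nothing describes batch entry. What is missing is the statement of that rule and the date needed to apply it.

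Other points on the same side also stand:

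- The ordering rule has an effect only if more than 500 patients enrol. That is possible but not certain.
- The percentages above measure delayed entry, not ordering. They would arise with a perfectly recorded ranking too.
- Ranking by consent date alone would not remove the bias, because past-storm patients who consent early would still be in the set.
- It would be too strong to say that retrospective patients cannot be identified, since the ES start date identifies those whose storm came before the registry.
- Consent forms at the centres may carry a date. The consent pages were not available for this review, so nothing firm can be said. A website timestamp is also conceivable, but the documents mention none, and it would show when a record was made rather than when the patient consented.

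None of this supplies the delay from ES to entry as a listed data item, or a plan to use it. The delayed-entry problem remains even if enrolment stops at exactly 500.

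**Conclusion.** The point holds as a gap in definition and data collection whose main effect is on the primary estimate. Followed as written, the plan pools survivors who entered late with new admissions, counts both from the ES, and does not list the date needed to separate or correct them.

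The direction is towards too low a mortality if late entrants otherwise carry the same risk. Under the one-year delay, a 20% share lowers 29.5% by 1.7 points and a 60% share by 5.2 points, against a sampling margin of about 4.0. These sizes rest on a constant 11% a year and on assumed shares and delays. The documents give neither, so the actual bias could be trivial or substantial. The ordering question alone would be a minor matter of missing detail. The change is worth making because it is cheap and affects what the study can conclude about mortality.

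**What to change.** 1. Add two fields to block "0.1 - General Data" of the case report form: the date of written consent, and the mode of entry (admitted with the index ES; past ES enrolled at a routine visit; retrospective, with the ES before the registry).
2. State in section 4 that the analysis set is the first 500 by date of consent, fixed before outcomes are tabulated. This has an effect only if more than 500 enrol.
3. State in section 4.4 that late entrants count as at risk only from their consent date (left-truncated Kaplan-Meier), with the ES kept as time zero.
4. Report the number of patients and 3-year mortality by entry mode. This also helps to check whether late entrants have similar risk once under observation, which the adjustment assumes.

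The cost is two fields, back-filling of records already entered, and somewhat wider intervals (in the illustration, ±4.1 to ±4.7 points instead of ±4.0). No visit or procedure is added for patients.

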4.1 PRIMARY ENDPOINT

- All-cause mortality 3 years after the ES

4.2 SECONDARY ENDPOINT

- Hospitalization for all causes 3 years after the ES

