4.3 ANALYSIS OF RELAPSES AND MORTALITY

Each center will be asked to report every new hospital admission of patients enrolled in the study and the cause of hospitalization. Moreover, data about subjects' vital status will be asked to be updated every 6 months.

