
4.0 - Follow Up
 
Last follow-up date  - Vital status at last follow-up  - Number of total ES recurrences  - First ES recurrence date  Number of total VT/VF recurrences  - First VT/VF recurrence date  - Number of total HF rehospitalizations  - First HF rehospitalization date 

 

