Attachment #4 – Follow-up requested data for the observational study

- Last follow-up date
- Vital status (alive, sudden cardiac death, non-sudden cardiac death, non-cardiac death, dead for unknown reasons)
- Total number of electrical storm recurrences
- First electrical storm recurrence date
- Total number of unclustered ventricular arrhythmia recurrences
- First unclustered ventricular arrhythmia recurrence date
- Total number of rehospitalization for heart failure
- First rehospitalization for heart failure

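### The secondary endpoint is all-cause hospitalization and section 4.3 asks for every admission, but the follow-up forms take only heart-failure rehospitalizations

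*Combined protocol and SAP*

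**What the plan says.** The only secondary endpoint, in section 4.2, is "Hospitalization for all causes 3 years after the ES". It serves aim (b) in section 2, which names mortality and rehospitalization as the two outcomes of the observational study and does not restrict the latter to heart failure (HF).

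On collection, section 4.3 states: "Each center will be asked to report every new hospital admission of patients enrolled in the study and the cause of hospitalization". It also asks for vital status to be updated every 6 months. Section 3.2 refers the reader to the CRF for what is collected: "For the type of data requested, see Case Report Form (attachment #3").

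The two admission fields in CRF block 4.0 (Follow Up) are "Number of total HF rehospitalizations" and "First HF rehospitalization date". Attachment #4, the follow-up list for the observational study, has "Total number of rehospitalization for heart failure" and "First rehospitalization for heart failure". Neither form has any other follow-up item about admissions.

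**The concern.** The endpoint and section 4.3 describe one outcome, admission for any cause, and the forms describe a narrower one, admission for HF. Section 3.2 makes the CRF the reference for requested data, and Attachment #4 was written for the very study that carries this endpoint. A center that completes both forms fully and correctly would still supply no information on a non-HF admission.

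Half of aim (b) is at stake. If the analysis uses the form data, the study reports HF rehospitalization in place of the endpoint it has declared. If the gap is noticed only at analysis, admission dates and causes would have to be recovered from many centers, up to 3 years after the events.

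**Working it through.** No figure in the plan is at issue, so the check compares the forms item by item with the endpoint.

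**Follow-up items**

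| Content | CRF block 4.0 | Attachment #4 |
|---|---|---|
| Last follow-up date, vital status | 2 | 2 |
| ES recurrence: count, first date | 2 | 2 |
| VT/VF (Attachment #4: unclustered arrhythmia) recurrence: count, first date | 2 | 2 |
| HF rehospitalization: count, first occurrence | 2 | 2 |
| Non-HF admission, cause of admission, or first all-cause admission date | 0 | 0 |
| Total | 8 | 8 |

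**Rest of the CRF.** Labelled fields by block, 0.1 to 4.0: 7 + 6 + 8 + 6 + 7 + 6 + 11 + 11 + 4 + 11 + 12 + 8 = 97. Three of the 97 concern hospital stay: the two HF fields above and the length of stay in block 2.1. The last sits with the data on the storm itself and is not a record of later admissions. The drop-down options cannot be seen in the text, but no field label refers to a non-HF admission.

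**Could other fields stand in?** The recurrence fields cannot. Section 1 notes that the device also records episodes with few or no symptoms, so a recurrence need not mean an admission, and an admission need not follow a recurrence.

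**What the form data would estimate.** Every HF admission is also an all-cause admission, so for each patient:

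- number of HF admissions ≤ number of all-cause admissions;
- first HF admission date ≥ first all-cause admission date;
- hence the 3-year proportion with an HF admission ≤ the 3-year proportion with any admission.

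A patient with an HF count above zero is known to have been admitted. A patient with an HF count of zero is not known to have been free of admission. The form data thus bound the endpoint from below and do not identify it.

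**How far section 4.3 closes the gap.** Section 4.3 makes two requests. Vital status has a field on both forms. Admission for any cause, with its cause, has a field on neither. The section names no other form and does not mention the admission date. Time to first all-cause admission, or placing an admission inside the 3-year window, needs that date.

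**Size.** Turning the bound into a number needs the ratio of all-cause to HF admissions, or an all-cause rate. The documents give neither. The 11% annual figure in section 4.4 is for death and does not help here.

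**A smaller mismatch.** In Attachment #4 the first HF item omits the word for date, while "First electrical storm recurrence date" and the unclustered-arrhythmia item include it. The CRF does ask for the HF date, so this is probably a wording slip, to be aligned at the same time.

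**The case against.** The strongest reply is that the data are requested. Section 4.3 asks in plain terms for all new admissions and their cause, and centers may well send dates with those reports. This stands as far as it goes. A reader of the forms alone might infer that all-cause admissions are never asked for, or that the data will certainly be lost, and the documents support neither. What is established is an inconsistency between the protocol text and its forms. Whether data are lost depends on how section 4.3 reports are sent and stored, which the protocol does not say. The reply does not remove the mismatch: if section 4.3 governs, the forms still need correcting to match it.

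A reader might also infer that section 4.4 plans a Kaplan-Meier curve for all-cause hospitalization that the forms could not support. Section 4.4 never mentions hospitalization, and its sentence on survival curves follows one on the primary endpoint and refers to a single endpoint, so it may mean mortality only. The point does not need that reading, because even a simple 3-year count or proportion of patients admitted for any cause cannot be obtained from the forms.

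It is also fair to say that consistency could be restored by narrowing section 4.2, section 4.3 and aim (b) to HF rehospitalization. That would be coherent, but it would give up the stated objective to save a few fields.

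**Conclusion.** The point holds as an internal inconsistency that should be fixed. The declared secondary endpoint is all-cause, and section 4.3 asks for the matching data, but 0 of 8 items in CRF block 4.0 and 0 of 8 in Attachment #4 can record a non-HF admission, its cause, or the date of a first all-cause admission. From the forms as written the study would obtain a lower bound on its endpoint, of unknown distance from the truth.

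Confidence is high on the mismatch, which rests on a direct count. It is lower on the consequence, which assumes that the analysis would draw on the forms, or that section 4.3 reports would arrive without a place to be recorded.

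The form gap does not affect the primary endpoint, since both forms carry vital status and the last follow-up date. It would be tempting to extend the point to the time origin, to survival to consent in retrospectively included patients, to the absence of a consent date on the CRF, or to death as a competing event. None of these follows from the HF-only fields. The time-origin and survival-to-consent questions bear on mortality as well, so they need separate treatment.

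**What to change.** Add to CRF block 4.0 and to Attachment #4 the date and cause of each new admission after the index ES stay. At minimum, add three items to each: the number of all-cause admissions, the date of the first, and its cause. State in section 4.3 that its admission reports are recorded in these fields and that the date is required. Add the missing date to the HF item in Attachment #4.

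The minimum option takes CRF block 4.0 from 8 to 11 fields (the whole CRF from 97 to 100) and Attachment #4 from 8 to 11 items. Recording every admission is more work over 3 years, but it is what section 4.3 already asks centers to report, apart from the date. Either option costs data entry only, with no added visits or procedures, so it fits the protocol's commitment to require none.

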4.3 ANALYSIS OF RELAPSES AND MORTALITY

Each center will be asked to report every new hospital admission of patients enrolled in the study and the cause of hospitalization. Moreover, data about subjects' vital status will be asked to be updated every 6 months.

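### The plan times all-cause hospitalization from the electrical storm but gives no stated route for recording non-heart-failure admissions between a past storm and enrolment, so the 3-year risk may be understated.

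*Combined protocol and SAP*

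**What the plan says.** - **Endpoint and clock.** Section 4.2 defines the secondary endpoint as "Hospitalization for all causes 3 years after the ES". Time runs from the storm, not from consent.
- **Late entry.** The registry inclusion criteria in section 3 state that "a patient with a previous episode of ES could also be enrolled during routine screening", with no limit on the time since that episode. Section 3.2 adds that "patients with an ES previous to the creation of this registry will be included retrospectively", subject to five conditions, one of which is consent at the next routine visit. Two others bear on completeness: "clinical data from the participating center are complete and accurate and allow to check inclusion and exclusion criteria", and "follow-up is available".
- **Analysis set.** Section 4 uses the first 500 registry patients and does not exclude those who entered after a past storm.
- **Admission reporting.** Section 4.3 asks each center to "report every new hospital admission of patients enrolled in the study and the cause of hospitalization". The same section says that "vital status will be asked to be updated every 6 months". It gives no interval for admissions.
- **Forms.** The follow-up page of the case report form (Attachment #3, item 4.0) and the list in Attachment #4 record the total number of heart-failure rehospitalizations and the first of them. Neither has an item for admissions from other causes.
- **Analysis.** Section 4.4 specifies Kaplan-Meier curves and log-rank tests, with possible subgroups. It does not mention delayed entry or how time before enrolment is handled.

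**The concern.** For a patient enrolled at the index storm, the endpoint clock and the reporting of admissions start together. For a patient enrolled a year or two later, the clock has been running throughout, but the instruction on admissions appears to begin at enrolment. A pneumonia or stroke admission in that interval belongs to the endpoint, yet no form field or instruction asks for it. If it goes unrecorded and the curve starts at the storm, the interval contributes person-time without its events.

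This is under-recording of a non-fatal event. It is separate from the requirement that a past-storm patient survive to consent.

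The error would not be spread evenly. Some centers may go back through the charts and others may not. The planned subgroups, including those by ICD programming, may differ in their share of past-storm patients. A subgroup with a larger share could look better for that reason alone.

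**Working it through.** **What the plan quantifies.** Its only projection is for deaths: 500 × 0.11 = 55 at one year and 500 × 0.11 × 3 = 165 at three years. Both reproduce, but neither concerns hospitalization. The plan gives no admission rate, past-storm share or lag, so the size of the problem can only be illustrated.

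**Routes by which an admission can reach the data**

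| Admission | After enrolment | Between a past storm and enrolment |
|---|---|---|
| Heart failure | Section 4.3 and the form fields | Form fields, which are not limited to time after enrolment |
| Any other cause | Section 4.3 instruction, but no form field | No stated route |

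The conditions in section 3.2 do not fill the last cell. The completeness condition is tied to checking eligibility, and the follow-up condition does not say what follow-up must contain. The section justifies retrospective inclusion by what ICDs record, and a device log does not hold all-cause admissions.

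**Assumptions for the illustration (none from the documents)**

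- Constant admission hazard *h* of 0.15, 0.30 or 0.50 per year, unchanged by earlier admissions.
- Past-storm share of 30%, all with the same lag *L* of 0.5, 1 or 2 years.
- No admission captured in the gap, and the gap treated as observed time.
- Deaths ignored.

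**Formulas**

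- True 3-year risk: 1 − exp(−3*h*).
- Risk that a past-storm patient can show: 1 − exp(−*h*(3 − *L*)).
- Cohort figure: 0.70 × true + 0.30 × shown.

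**Worked case, *h* = 0.30**

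- True risk: 1 − exp(−0.90) = 59.3%.
- *L* = 1: shown risk 1 − exp(−0.60) = 45.1%; cohort figure 0.70 × 59.3 + 0.30 × 45.1 = 55.1%.
- *L* = 2: shown risk 1 − exp(−0.30) = 25.9%; cohort figure 0.70 × 59.3 + 0.30 × 25.9 = 49.3%.

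**Understatement of the cohort figure, in percentage points**

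| *h* per year | True risk | *L* = 0.5 | *L* = 1 | *L* = 2 |
|---|---|---|---|---|
| 0.15 | 36.2% | 1.5 | 3.1 | 6.7 |
| 0.30 | 59.3% | 2.0 | 4.3 | 10.0 |
| 0.50 | 77.7% | 1.9 | 4.3 | 11.5 |

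**Sensitivity to the assumptions.** A separate grid with true risk of 40 to 70%, a past-storm share of 10 to 50% and the same lags gives 0.5 to 18.5 points. In the other direction, any capture in the gap shrinks the figures. If a fraction *c* of gap admissions is recorded, *L* is replaced by (1 − *c*)*L* in the formula. Recording half the admissions in a 2-year gap is then equivalent to a 1-year gap with none recorded: 4.3 points instead of 10.0 at *h* = 0.30.

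**The case against.** A reader might infer something stronger: that centers report admissions only from enrolment onward, that everything before is lost, and that the gap is counted as admission-free. The documents do not support that in full.

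- Heart-failure admissions in the gap do have a route. The form fields ask for their number and first date without restricting them to the time after enrolment.
- Section 4.3 does not exclude earlier admissions. Being enrolled may identify the patient rather than the calendar window, and a new admission could mean new since the storm. That would fit the endpoint in section 4.2.
- Retrospective patients must have follow-up available. For a past storm this could well mean follow-up since that storm.
- Section 4.4 is silent on time before enrolment. Treating it as event-free is an inference from a storm origin combined with ordinary Kaplan-Meier.
- It is also tempting to contrast active collection of vital status with passive collection of admissions. Section 4.3 asks centers for both. The difference is that only vital status has a stated interval.

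All of this stands, and it limits the claim. It does not remove it. No reading supplies a form field for other admissions in the gap or tells a center to look back for them. The absence of an all-cause field affects newly enrolled patients too, and adding one would not close the gap unless centers were told to complete it back to the storm.

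**Conclusion.** The point holds in a conditional form. The plan does not say how non-heart-failure admissions between a past storm and enrolment enter the data, nor how that time is analysed. If the plan is followed on its most natural reading, the 3-year all-cause admission risk would tend to be too low, and comparisons between groups with different past-storm shares would be distorted.

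The illustrated 1.5 to 11.5 points rests wholly on assumed hazard, lag and share, with no capture in the gap and no deaths. It shows what is plausible and does not estimate the bias in this study. Partial capture, including that of heart-failure admissions, would make it smaller. A larger past-storm share or a longer lag could make it larger.

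The change should be made: this is the study's only secondary endpoint, and rehospitalization is named in its aim. This recording gap does not touch the primary mortality endpoint.

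**What to change.** 1. **Record back to the storm.** In section 4.3, Attachment #3 and Attachment #4, add an all-cause admission item (date and cause of each admission) covering the time since the ES. For any patient enrolled after the index episode, complete it retrospectively at consent.
2. **Ask at each update.** Add to the 6-monthly vital-status update: any admission since the last update, yes or no, with dates and cause. Require an explicit no, so that silence is not read as no admission.
3. **State the analysis rule in section 4.4.** Where the record since the ES is incomplete, leave the patient out of the storm-origin first-admission curve, or report time from enrolment separately. Show the result in patients enrolled at the index ES as a sensitivity analysis.
4. **Limit delayed entry.** Use it only for patients confirmed admission-free at enrolment. Applied where earlier admissions are unknown, it would put patients who have already had the event into a first-event risk set.

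The cost is a short addition to the text, a few form lines at contacts already planned, a little extra chart work for past-storm patients, and somewhat fewer patients in the storm-origin curve.
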